Photography of both hands back and front including the wrist ¹⁶		X					X	X		X						8.1.4
End of treatment/trial																_
End-of-treatment form										X						8.10.1
End-of-trial form ¹⁷										(X)	X	X		(X)	(X)	8.10.2

- 1. End-of-treatment assessments will be conducted at Week 24. Participants who permanently discontinue the IMP or who withdraw from the trial prior to Week 24 will be asked to return to the trial site for an ET visit as soon as possible after the last dose for completion of all trial procedures scheduled for the visit at Week 24.
- 2. All participants will be asked to return to the trial site approximately 2 weeks after the last dose of IMP for assessment of safety at a follow-up visit.
- 3. For WOCBP treated with alitretinoin, only.
- 4. Participants who permanently discontinue the IMP prior to Week 12 will be asked to return to the trial site at Week 12 for a primary endpoint visit and at Week 24 for a nominal Week 24 visit. Participants who permanently discontinue the IMP between Week 12 and Week 24 will be asked to return to the trial site for a nominal Week 24 visit.
- 5. Unscheduled visits occur if participants need to make a visit in between the scheduled visit dates, e.g. for reading of a patch test, due to an AE, or due to a significant change in their disease state. Assessments to be performed at unscheduled visits will be at the discretion of the unblinded investigator.
- 6. For participants treated with medications requiring a 28-day washout period prior to baseline (see Table 6-2), the duration of the screening period may be extended up to 31 days to ensure appropriate washout. For WOCBP the duration of the screening period may be extended up to 42 days to ensure compliance with contraceptive and pregnancy prevention programme requirements.
- 7. For participants who have not had a patch test within 3 years prior to screening, the patch test should be completed so results are available prior to baseline assessments (Day 1).

- 8. Completion of the HESD component of the eDiary will be initiated at least 1 week prior to baseline (Day 1), but preferably from the date the participants receive the eDiary. Compliance with the eDiary completion will be reviewed by the trial site staff throughout the trial. Participants who permanently discontinue the IMP but remain in the trial will continue completing the eDiary until the nominal Week 24 visit.

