- 9. Not applicable at the ET visit if the participant does not withdraw from the trial, as participants who discontinue IMP but remain in the trial will continue completing the eDiary until the nominal Week 24 visit.
- 10. Includes Itch PGI-S, Pain PGI-S, and HESD PGI-S.
- 11. Includes Itch PGI-C, Pain PGI-C, and HESD PGI-C.
- 12. While on treatment with delgocitinib cream 20 mg/g, local tolerability will be evaluated weekly by the participants in the eDiary from Day 7 onwards up to End of Treatment/Early Termination visit.
- 13. Participants should be fasting for at least 8 hours prior to collection of laboratory samples.
- 14. For WOCBP treated with delgocitinib, only.
- 15. After baseline, mental health interview is required only for the alitretinoin group.
- 16. Photography will require additional informed consent. If deemed necessary (e.g. in case of poor quality), photographs can be retaken at the next visit.
- 17. An end-of-trial form must be completed for all screened participants at the participant's last trial visit. For participants who discontinue IMP prematurely, the end-of-trial form will be completed at the nominal Week 24 visit, if this visit occurs after Visit 11 or Visit 12 (if applicable). For WOCBP treated with alitretinoin, the end-of-trial form must be completed at Visit 12 (pregnancy follow-up). For all other participants, the end-of-trial form must be completed at Visit 11 (follow-up).

Abbreviations: AE=adverse event; CHE=chronic hand eczema; DLQI=Dermatology Life Quality Index: ECG=electrocardiogram; eDiary=electronic diary; EQ-5D-5L=EuroQoL 5-Dimension Health Questionnaire 5-Level; EOT= end-of-treatment; ET=early termination; HECSI=Hand Eczema Severity Index; HEIS=Hand Eczema Impact Scale®; HESD=Hand Eczema Symptom Diary®; IGA-CHE=Investigator's Global Assessment for chronic hand eczema®; IgE=immunoglobulin E; IMP=investigational medicinal product; PGI-C = Patient Global Impression of Change; PGI-S = Patient Global Impression of Severity; TSQM=Treatment Satisfaction Questionnaire for Medicine; WOCBP=woman of childbearing potential; WPAI-CHE=Work Productivity and Activity Impairment – Chronic Hand Eczema.

2 Introduction

Delgocitinib is a pan-Janus kinase (JAK) inhibitor that is being developed as a cream for the treatment of inflammatory skin disorders, such as CHE.

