2.3.3 Overall Benefit/Risk Conclusion

Taking into account the measures taken to minimise risk for the trial participants, the potential risks identified in association with delgocitinib and alitretinoin are justified by the anticipated benefits that may be afforded to participants with severe CHE, and more generally the potential benefits to patients with moderate to severe CHE in the future.

3 Objectives and Endpoints

Table 3-1 Primary Objective and Estimands for Primary Endpoint and Key Secondary Endpoints

Objectives	Estimand type and strategy	Endpoints
Primary objective: To compare the efficacy and health-related quality of life of twice-daily topical application of delgocitinib cream with once-daily oral administration of alitretinoin capsules in the treatment of patients with severe CHE.	Primary. 'Composite' strategy. First supplementary. 'Pandemic modified composite' strategy. Second supplementary (for endpoints at Week 12 and Week 24). 'Treatment policy' strategy.	Primary endpoint: Change in HECSI score from baseline to Week 12. Key secondary endpoints: HECSI-90 at Week 12. IGA-CHE TS at Week 12. Change in HESD itch score (weekly average) from baseline to Week 12. Change in HESD pain score (weekly average) from baseline to Week 12. AUC of HECSI-90 from baseline up to Week 24. AUC of change from baseline in DLQI score up to Week 24. Change in HECSI score from baseline to Week 24.

Abbreviations: AUC=area under the curve; CHE=chronic hand eczema; DLQI=Dermatology Life Quality Index; HECSI=Hand Eczema Severity Index; HECSI-90=at least 90% improvement in HECSI score from baseline; HESD=Hand Eczema Symptom Diary©; IGA-CHE=Investigator's Global Assessment for chronic hand eczema©; IGA-CHE TS=IGA-CHE treatment success.

Table 3-2 Secondary and Exploratory Objectives and Endpoints

Objectives	Endpoints				
Secondary objective: To compare the safety of twice-daily topical application of delgocitinib cream with once-daily oral administration of alitretinoin capsules in the treatment of patients with severe CHE.	 Secondary endpoints: Number of treatment-emergent AEs from baseline up to Week 26. Number of treatment-emergent SAEs from baseline up to Week 26. Number of AEs leading to IMP discontinuation up to Week 24. 				
Exploratory objectives:	Exploratory endpoints:				

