To compare the efficacy and health-related quality of life of twice-daily topical application of delgocitinib cream with once-daily oral administration of alitretinoin capsules in the treatment of patients with severe CHE.	 Efficacy: IGA-CHE TS at Week 24. HECSI-75 at Week 12 and Week 24. HECSI-90 at Week 24. Change in HESD itch score (weekly average) from baseline to Week 24. Reduction of HESD itch score (weekly average) of ≥3 points ¹ at Week 12 and Week 24 AUC from baseline to Week 24 of reduction of HESD 				

Objectives	Endpoints
	itch score (weekly average) of ≥3 points ¹ .
	• Reduction of HESD itch score (weekly average) of ≥4 points ² at Week 12 and Week 24
	• AUC from baseline to Week 24 of reduction of HESD itch score (weekly average) of ≥4 points ² .
	Change in HESD pain score (weekly average) from baseline to Week 24.
	• Reduction of HESD pain score (weekly average) of ≥3 points ³ at Week 12 and Week 24.
	• AUC from baseline to Week 24 of reduction of HESD pain score (weekly average) of ≥3 points ³ .
	• Reduction of HESD pain score (weekly average) of ≥4 points ⁴ at Week 12 and Week 24.
	AUC from baseline to Week 24 of reduction of HESD pain score (weekly average) of ≥4 points ⁴ .
	Change in HESD score (weekly average) from baseline to Week 12 and Week 24.
	 Reduction of HESD score (weekly average) of ≥3 points ⁵ at Week 12 and Week 24.
	 Reduction of HESD score (weekly average) of ≥4 points ⁶ at Week 12 and Week 24.
	Health-related quality of life:
	Change in DLQI score from baseline to Week 12 and Week 24.
	• Reduction of DLQI score of ≥4 points ⁷ at Week 12 and Week 24.
	DLQI score of 0 or 1 at Week 12 and Week 24.
	Change in HEIS (individual domains and total score) from baseline to Week 12 and Week 24.
	Change in EQ-5D-5L index score from baseline to Week 12 and Week 24.
	Change in EQ-5D-5L visual analogue scale score from baseline to Week 12 and Week 24.
To evaluate the effect of twice-daily topical	TSQM at Week 12 and at Week 24.
application of delgocitinib cream on treatment satisfaction and work productivity compared with once-daily oral administration of alitretinoin capsules in the treatment of patients with severe CHE.	Change in WPAI-CHE (each individual domain) score from baseline to Week 12 and Week 24 ⁸ .
To compare the safety of twice-daily topical application of delgocitinib cream with once-daily	• Number of events of increased levels of triglycerides >3.42 mmol/L (fasted state) up to Week 26.

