Safety assessments, adverse events, and treatment decisions will be made by the unblinded investigator to allow for:

- Dose reductions for participants treated with alitretinoin (Section 6.5).
- Permanent IMP discontinuation (Section 7.1).
- Decisions to continue, stop or restart the IMP from Week 16 for delgocitinib or Week 12 for alitretinoin (Section 6.5.1).

Participants will stop the IMP if they achieve an IGA-CHE score of 0 (clear) or 1 (almost clear) after 16 weeks of delgocitinib treatment or 12 weeks of alitretinoin treatment. Participants who discontinued delgocitinib treatment due to IGA-CHE score of 0 or 1 must restart treatment if they relapse to an IGA-CHE score of ≥2. These participants will continue attending the treatment period visits as planned until Week 24.

Participants who permanently discontinue the IMP will attend an ET visit, they will stop attending the treatment period visits and will only be asked to return to the trial site at Week 12 for a primary endpoint visit and at Week 24 for a nominal Week 24 visit.

Follow-up period: Approximately 2 weeks after the last dose of IMP, participants will attend a follow-up visit for safety assessments. Women of childbearing potential treated with alitretinoin will attend an additional follow-up visit for a pregnancy test, 5 weeks after the last dose of alitretinoin

Refer to Section 10.5 for coronavirus disease 2019 (COVID-19) pandemic contingency plan.

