8.3.1 Time Period and Frequency for Collecting AE and SAE Information

All AEs and SAEs will be collected from the signing of the ICF until the end of trial (defined as attending the last visit in the trial [the ET visit, the nominal Week 24 visit, or the last follow-up visit, whichever comes last]), at the timepoints specified in the SoA (Table 1-1).

It will be recorded in the eCRF if the AE started prior to first administration of IMP.

All SAEs will be recorded and reported to the sponsor immediately without undue delay but no later than within 24 hours of awareness, as indicated in Appendix 3. The investigator will submit any updated SAE data to the sponsor within 24 hours of it being available.

Investigators are not obliged to actively seek information on new AEs or SAEs after the conclusion of trial participation. However, if the investigator learns of any SAE, including a death, at any time after a participant has been discharged from the trial, and he/she considers the event to be reasonably related to the IMP or trial participation, the investigator must promptly notify the sponsor.

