9.3.11.3 Clinical Laboratory Evaluation

For laboratory parameters, the absolute values as well as the changes from baseline will be summarised by visit for each treatment group.

A shift table will be produced for relevant parameters showing the categories at baseline against those at each post-baseline visit.

For participants with post-baseline values, the number of events reported up to Week 26 will be summarised. For the following laboratory abnormalities endpoints, binary estimand strategy will be applied, as described in Section 9.3.6.3:

- Increased levels of triglycerides >3.42 mmol/L (fasted state).
- Increased levels of cholesterol >7.75 mmol/L (fasted state).
- Increased levels of ALT and/or AST >3×ULN (or >3×baseline if baseline was abnormal but <2×ULN).
- Increased levels of ALP > 2.5 × ULN.
- Increased levels of bilirubin >1.5×ULN up to Week 26.

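### Laboratory-event endpoints run to Week 26, but scheduled sampling of permanent discontinuers ends about 2 weeks after their last dose, and the analysis does not account for the unsampled time

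*Combined protocol and SAP*

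**What the plan says.** Section 3, Table 3-2, lists the secondary safety endpoint "Number of treatment-emergent AEs from baseline up to Week 26", with the same window for SAEs. The exploratory laboratory endpoints follow suit, for example "Number of events of increased levels of triglycerides >3.42 mmol/L (fasted state) up to Week 26". Section 9.3.11.3 states: "For participants with post-baseline values, the number of events reported up to Week 26 will be summarised". It then applies the binary estimand strategy of Section 9.3.6.3 to the five laboratory abnormalities, that is, a stratified difference in proportions.

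The schedule is built on the last dose. Footnote 2 of Table 1-1 reads: "All participants will be asked to return to the trial site approximately 2 weeks after the last dose of IMP". Section 4.1 says of participants who permanently discontinue that "they will stop attending the treatment period visits and will only be asked to return to the trial site at Week 12", and then for the nominal Week 24 visit. In Table 1-1 the AE row is marked at both of those visits. The fasting-lipid row and the chemistry/haematology row are blank at both.

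Under Section 8.3.1, AE collection ends at the ET visit, "the nominal Week 24 visit, or the last follow-up visit, whichever comes last". Section 9.3.11.1 gives AEs a rate per 100 patient-years observed. Section 9.3.11.3 gives no such rate for laboratory events.

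**The concern.** A laboratory event can be seen only if a sample is taken. When the endpoint names Week 26 but scheduled sampling stops with treatment, a participant with no event on record may have been event-free to Week 26 or may simply not have been sampled. The two are counted alike.

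This matters because the purpose is a between-arm safety comparison, and the rules that end treatment are not the same in the two arms. In Section 7.1, criterion 8 (IGA-CHE score of 4) takes effect after 12 weeks of alitretinoin but 16 weeks of delgocitinib. Criteria 6 and 7 apply to alitretinoin only, and criterion 7 includes lipids that cannot be controlled. Stopping, and with it the end of sampling, can therefore depend on the arm and on the outcome being counted.

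**Working it through.** **Where Week 26 comes from.** Table 1-1 puts end of treatment at Day 169. Adding 14 days gives Day 183, and (183 − 1)/7 = 26.0 weeks. The figure reproduces, but only for a last dose at about Week 24.

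**Window after permanent discontinuation.** Let *w* be the week of the last dose.

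- Last scheduled laboratory sample (Visit 11): *w* + 2.
- Unsampled part of the 26 weeks: 26 − (*w* + 2) = 24 − *w*.
- End of AE collection for a participant who stays in the trial: the later of 24 and *w* + 2.

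| Last dose (week) | Last scheduled sample | Unsampled weeks | Share of 26 | AE collection to |
|---|---|---|---|---|
| 4 | 6 | 20 | 77% | 24 |
| 8 | 10 | 16 | 62% | 24 |
| 12 | 14 | 12 | 46% | 24 |
| 16 | 18 | 8 | 31% | 24 |
| 20 | 22 | 4 | 15% | 24 |
| 24 | 26 | 0 | 0% | 26 |

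The AE shortfall is thus at most 2/26 = 7.7% per retained discontinuer. Women of childbearing potential on alitretinoin also have Visit 12 at *w* + 5. Under Section 8.3.1 that carries AE collection to Week 25 for *w* = 20 and Week 26 for *w* = 21, although Table 1-1 marks no AE assessment at Visit 12.

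**Difference built into the rules.** For participants stopped under criterion 8, scheduled samples end at 12 + 2 = Week 14 on alitretinoin and 16 + 2 = Week 18 on delgocitinib, a gap of 4 weeks.

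**Possible size across arms (assumed rates).** The documents state no discontinuation rates. With a proportion *d* stopping permanently at week *w* and all others sampled to Week 26, the mean laboratory window is (1 − *d*) × 26 + *d* × (*w* + 2). Take *w* = 10 and 10% on delgocitinib: 0.9 × 26 + 0.1 × 12 = 24.6 weeks. For alitretinoin:

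- 10%: 24.6 weeks, no gap.
- 20%: 0.8 × 26 + 0.2 × 12 = 23.2 weeks, 5.7% shorter.
- 30%: 0.7 × 26 + 0.3 × 12 = 21.8 weeks, 11.4% shorter.
- 40%: 0.6 × 26 + 0.4 × 12 = 20.4 weeks, 17.1% shorter.

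At 40% against 10%, moving the last dose from Week 6 to Week 16 changes the gap from 22.3% to 9.5%. The matching AE gap is 1 − 25.2/25.8 = 2.3%.

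**Does the binary analysis absorb this?** No. Section 9.3.6.3 compares proportions by stratum and imputes non-response after an intercurrent event. Section 9.3.11.3 does not say whether non-response means event or no event here. Under either reading, time under sampling does not enter.

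**Participants who stop for IGA-CHE 0 or 1.** Section 4.1 keeps them in the treatment-period visits to Week 24, laboratory samples included. What is unclear is Visit 11. Read literally it falls at about Week 14 (alitretinoin) or Week 18 (delgocitinib) if they never restart, which is known only at Week 24. Section 8.3.1 does not name Visit 10 among the visits that can end AE collection. Footnote 17 opens with the last trial visit as the general rule but closes by assigning the end-of-trial form to Visit 11.

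**The case against.** Sampling to 2 weeks after the last dose is a usual safety window, and Week 26 can be read as an outer bound: 24 weeks of treatment plus 2 of follow-up. The laboratory endpoints are exploratory and lie outside the confirmatory hierarchy. Unscheduled samples are possible, Appendix 6 requires repeat sampling for marked liver abnormalities, and AEs of hypertriglyceridaemia, hypercholesterolaemia and liver toxicity are still collected at the nominal Week 24 visit. Section 9 calls itself a summary and leaves technical detail to a SAP; no separate SAP text was available for this check, so a laboratory rate may be defined there.

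Much of this stands and keeps the point modest. It does not close the gap. If the intended window follows the last dose, the endpoint should say so. Unscheduled and liver-triggered samples are not a systematic schedule, and clinical AE reports do not replace a threshold count.

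Stronger readings are tempting but not supported:

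- **The AE and SAE endpoints are seriously under-observed.** The loss is normally at most 2 of 26 weeks per retained participant, and a rate per observed time is planned.
- **Everyone who stops before about Week 22 leaves AE collection at Week 24.** Visit 12 is an exception for some women on alitretinoin.
- **Responders lose their laboratory follow-up.** They keep it to Week 24.
- **The laboratory endpoints are left as raw counts.** A binary analysis is planned.
- **The stated 25-week minimum duration proves that some participants have no Week 26 contact.** It equals 1 + 24, but the same section lists 2 to 5 weeks of follow-up, so it may be a slip for 1 + 24 + 2 = 27.
- **Counts will be lower in the arm that stops earlier.** This is possible, not shown: no rates are given, stopping may follow the very event counted, and fewer later events may reflect less exposure.

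**Conclusion.** The point holds for the five laboratory-event endpoints. The stated window reaches Week 26, the scheduled window for a permanent discontinuer ends at last dose plus 2 weeks, and the planned analysis does not adjust for the difference. For an individual the unsampled share runs from 0% (last dose at Week 24) to 77% (Week 4). Between arms the size is unknown. The 17% figure rests on assumed stopping of 40% against 10% at Week 10; with equal rates and timing the gap is zero. The arm-specific stopping rules make a difference plausible without establishing its direction or amount. For AEs and SAEs the matter is one of wording. This is an inexpensive improvement to the safety comparison and does not touch the efficacy conclusions.

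**What to change.** 1. In Table 3-2 and Section 9.3.11.3, define the laboratory-event window as up to the last scheduled sample (Visit 10 or Visit 11, whichever is later).
2. Alongside the planned binary analysis, report by arm the participants with at least one event per 100 patient-years of sampled time, counting time to the first event or the last sample.
3. Keep Week 26 as the outer bound for the AE and SAE endpoints, so that follow-up after treatment stays in the endpoint. State that participants who stop early are normally observed to Week 24, and use the rate already planned in Section 9.3.11.1 for the between-arm AE comparison.
4. Reconcile footnote 17, Section 8.3.1 and the timing of Visits 11 and 12 for participants who stop for IGA-CHE 0 or 1 and do not restart. Also reconcile Section 8.3.1 with the missing AE mark at Visit 12.

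The cost is one extra table per laboratory endpoint (five in all) and slightly longer endpoint wording. No visit or sample is added.
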